**Table 2: Visit Windows for CBC with differential, Complete serum chemistry, C-reactive protein, Ferritin and LDH.**

Analysis Visit Name	Target Visit Day	Study Day Range in Window
----------------------------	-------------------------	----------------------------------

Baseline	Day 1	Prior to first dosing (prior to or on Day 1 if exact dosing time is not available)
Day 3	Day 3	Day 2 to 3
Day 5	Day 5	Day 4 to 6
Day 8	Day 8	Day 7 to 9
Day 12	Day 12	Day 10 to 13
Day 15	Day 15	Day 14 to 16
Day 19	Day 19	Day 17 to 20
Day 22	Day 22	Day 21 to 23
Day 26	Day 26	Day 24 or later
NOTE: Day 1 is the date of first selinexor or placebo. Analysis visit and visit window may change for certain parameters depending on the data availability.		

**Table 3: Visit Windows for PT, aPTT, INR, CCI**

Analysis Visit Name	Target Visit Day	Study Day Range in Window
Baseline	Day 1	Prior to first dosing (prior to or on Day 1 if exact dosing time is not available)
Day 3	Day 3	Day 2 to 3
Day 5	Day 5	Day 4 to 6
Day 8	Day 8	Day 7 to 9
Day 12	Day 12	Day 10 to 13
Day 15	Day 15	Day 14 to 18
Day 22	Day 22	Day 19 to 23
Day 26	Day 26	Day 24 or later
NOTE: Day 1 is the date of first selinexor or placebo. Analysis visit and visit window may change for certain parameters depending on the data availability.		

**Table 4: Visit Windows for Cells for Leukocyte Phenotyping**

Analysis Visit Name	Target Visit Day	Study Day Range in Window
Baseline	Day 1	Prior to or on Day 4
Day 8	Day 8	Day 5 to 9/11
Day 12/15	Day 12 or Day 15	Day 10/12 or later
NOTE: Day 1 is the date of first selinexor or placebo. Analysis visit and visit window may change for certain parameters depending on the data availability.		

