### **5.3. Missed or Vomited Doses of Selinexor**

#### **5.3.1. Missed Doses of Selinexor**

Missed selinexor doses should be managed as follows:

- If a dose was missed, the dose should be taken the next day. Subsequent doses must respect the required 48 hour interval planned schedule. All missed and delayed doses should be documented
- If a dose must be skipped (e.g., due to recommendation of treating physician), the next dose will be taken as per schedule. All missed and delayed doses should be documented.

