## 2. STUDY DESIGN

### 2.1 Overview of Study Design

This is a randomized phase 2 single-blinded study of low dose selinexor versus placebo to evaluate the activity and safety, as well as reduction in mortality in patients with severe COVID-19.

A dose of 20 mg selinexor or matching placebo will be administered orally on Days 1, 3, and 5 of each week for up to 2 weeks. If the patient is tolerating therapy and clinically benefitting, dosing can continue for an additional 2 weeks.

The study population will consist of hospitalized patients  $\geq 18$  years old with COVID-19.

The randomization under protocol version 6.0 or above will be stratified by:

- Use of concomitant therapies
  - Use of anti-viral (e.g. remdesivir) only
  - Use of anti-inflammatory (e.g. hydroxychloroquine, biologics targeting e.g. IL-6 or IL-1) only
  - Use of both anti-viral and anti-inflammatory therapies
  - Use of neither anti-viral nor anti-inflammatory therapy
- Number of high-risk comorbidities.
  - No high-risk comorbidity
  - One high-risk comorbidity
  - Two or above comorbidities

[figure not shown]
High risk comorbidities are defined as: BMI > 30, cancer patients on chemotherapy, patients with cardiac (CAD, AMI, CHF) or pulmonary (COPD, emphysema) disease, diabetes, hypertension.

Note: acetaminophen and nonsteroidal anti-inflammatory drugs (NSAIDs) will not constitute anti-inflammatory agents for the purposes of stratification.

The study schedules are presented in Table 1 of the protocol.

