### **4.3 Definition of Baseline**

For all evaluations unless otherwise noted, baseline is defined as the most recent non-missing measurement prior to the first administration of study treatment. Baseline can be the same date as first dose, given the measurement is expected prior to first dose when only date information is available.

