### **4.5 Visit Windows**

For safety data that are summarized/plotted by time points, non-missing assessments from all scheduled and unscheduled visits will be mapped to the nearest visit. Analysis visit windows for clinical laboratory parameters are defined in Table 2 to Table 4. If there are 2 or more assessments mapped to the same analysis visit for a patient, the assessment that is closest to the target visit day will be used for analysis. If there are 2 or more assessments mapped to the same analysis visit with the same distance from the target visit day, then select the latest one for the analysis. Visit windows definitions will be described in analysis data specifications.

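### SAP Table 4 sets the leukocyte phenotyping baseline window without a pre-dose condition, so in limited cases a post-dose sample can become baseline

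*SAP*

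**What the plan says.** SAP 4.3 sets the default. It opens with "For all evaluations unless otherwise noted" and continues that "baseline is defined as the most recent non-missing measurement prior to the first administration of study treatment". It also lets a measurement on the first-dose date count as baseline when only the date is known, on the footing that it was expected before dosing.

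SAP 4.5 then gives windows by type of laboratory parameter. Tables 2 and 3 define the Baseline row as "Prior to first dosing (prior to or on Day 1 if exact dosing time is not available"). Table 4, for leukocyte phenotyping, gives the row a target of Day 1 and the window "Prior to or on Day 4". The footnote to Table 4 fixes the time origin: "NOTE: Day 1 is the date of first selinexor or placebo".

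Where several samples fall in one window, SAP 4.5 says "the assessment that is closest to the target visit day will be used for analysis", and equal distances are resolved in favour of the latest sample. Scheduled and unscheduled samples are both mapped.

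Protocol Table 1 schedules phenotyping blood at Screening (Day -2 to Day 1), at Day 1, at Day 8, and at Day 12 or Day 15. The Day 1 column carries a tolerance of one day either way, and no pre-dose timing is stated for that draw.

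**The concern.** A baseline is meant to describe the patient before treatment. Table 4 admits samples through Day 4 when dosing starts on Day 1, and it drops the pre-dose condition that the two neighbouring tables carry. Nothing in the readable SAP describes the row as a deliberate exception or gives a reason for it.

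If a post-dose sample becomes baseline, whatever the drug has already done to the immune cells is built into the reference value and disappears from any later change score. Placebo patients have no drug effect to lose, so a comparison of changes between arms would be pulled towards no difference, to the extent that such samples are used.

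**Working it through.** **1. The three Baseline rows side by side**

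- Tables 2 and 3: before first dosing. A Day 1 sample is accepted by date only when the dosing time is missing.
- Table 4: any time up to and including Day 4, with no reference to dosing.
- SAP 4.3: before first dosing, unless otherwise noted.

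The Day 4 limit can be reproduced as a midpoint. Between the Day 1 and Day 8 targets it is (1 + 8)/2 = 4.5, so Day 4 goes to Baseline and Day 5 to Day 8. The next boundary fits the same pattern: (8 + 15)/2 = 11.5 gives the 11/12 split, and (8 + 12)/2 = 10 is where the alternative 9/10 split falls. My inference is that Table 4 is a nearest-visit partition to which the pre-dose override of Tables 2 and 3 was not added.

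**2. Doses that can precede a sample in the window**

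SAP 2.1: "A dose of 20 mg selinexor or matching placebo will be administered orally on Days 1, 3, and 5 of each week". On nominal days, the doses given by the end of Days 1, 2, 3 and 4 number 1, 1, 2 and 2. Protocol 5.3.1 says of the doses after a missed one: "Subsequent doses must respect the required 48 hour interval planned schedule". If that spacing is kept throughout and each visit may move by one day, a post-dose sample on Days 1 to 4 still follows one or two doses. (If doses one day apart were allowed, which I do not assume, the count by the end of Day 4 could be three.)

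**3. Which sample the SAP 4.5 rule selects**

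Take one pre-dose and one post-dose sample, with target Day 1. SAP 4.2 has no Day 0, and SAP 4.5 does not say whether distance is counted in study-day numbers or calendar days, so both are shown. A post-dose sample on Day 1, 2, 3 or 4 lies at distance 0, 1, 2 or 3 on either count.

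| Pre-dose sample | Distance, by number / calendar | Post-dose sample selected (by number) | Post-dose sample selected (calendar) |
|---|---|---|---|
| Day -2 | 3 / 2 | Days 1, 2, 3; Day 4 on a tie | Days 1, 2; Day 3 on a tie |
| Day -1 | 2 / 1 | Days 1, 2; Day 3 on a tie | Day 1; Day 2 on a tie |
| Day 1 | 0 / 0 | Day 1 only, on a tie | Day 1 only, on a tie |

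On either count, a Day 2 post-dose draw displaces a screening sample from Day -2 or Day -1. A Day 1 pre-dose sample is kept against every Day 2, 3 or 4 sample and can be displaced only by a later sample on Day 1 itself. If there is no pre-dose sample at all, any sample through Day 4 is taken as baseline.

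**4. Set against the schedule**

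No phenotyping draw is scheduled on Day 3 or Day 4. The realistic routes are a Day 1 draw taken after the dose, a Day 1 draw slipping to Day 2, or an unscheduled sample. The first two follow one dose. A baseline after two doses would normally need an unscheduled draw.

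**5. Size of the effect**

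If a fraction f of a patient's eventual drug-related change has occurred by the baseline sample, the change score shows 1 - f of it. If a share p of an arm is affected and the true changes are alike, the arm mean is multiplied by 1 - p × f. The documents give neither p nor f. Each can lie anywhere from 0 to 1, so the multiplier is not determined.

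**The case against.** **Exception clause.** A reader might infer that Table 4 breaches SAP 4.3. The documents do not go that far. SAP 4.3 yields to exceptions noted elsewhere, and Table 4 may be such an exception or may only be a set of visit bins, with 4.3 still supplying the baseline value. This stands against calling it a breach. It does not remove the inconsistency: the row is labelled Baseline, differs from Tables 2 and 3, and does not say which reading applies.

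**Protection from the selection rule.** A reader might infer that choosing the sample nearest Day 1 gives no protection. It does: any patient with a Day 1 pre-dose sample is safe from Day 2 to 4 samples. The gap is confined to patients without one and to ties on Day 1.

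**Visit tolerance.** If the whole Day 1 visit moves, the first dose moves with it and so does Day 1. A Day 2 draw therefore arises only when the blood draw is separated from the dose. That narrows the route. Protocol Table 1 does not close it, because it states no pre-dose timing for this draw.

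**No visible analysis.** The readable SAP contains no change-from-baseline analysis of phenotyping. SAP 7.2.2.1 covers CRP, ferritin, LDH and cytokines, and SAP 8.2 covers hematology, chemistry and coagulation. SAP 7.3 is redacted and may hold its own rule. This stands in full and limits what can be said about consequences.

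**Windows may change.** The Table 4 footnote lets windows change with data availability. That restores no pre-dose condition.

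**Conclusion.** The inconsistency is real and small. As written, Table 4 allows a post-dose phenotyping sample to serve as baseline when there is no Day 1 pre-dose sample, or when a later Day 1 sample ties with it.

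Two stronger readings are not supported. One is that two of the six first-course doses would ordinarily precede baseline; the schedule has no draw on Day 3 or 4. The other is a specific attenuation, such as a halved effect; that would only restate an assumed f of one half.

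The number of patients affected is unknown, and whether this baseline feeds a change score cannot be seen. The primary endpoint and the visible secondary endpoints are not affected. The conclusion about the wording rests on the text alone. The one-or-two-dose count also assumes the 48-hour spacing in Protocol 5.3.1.

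**What to change.** Replace the Baseline cell of SAP Table 4 with the wording of Tables 2 and 3: "Prior to first dosing (prior to or on Day 1 if exact dosing time is not available").

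Add a sentence that post-dose phenotyping samples through Day 4 are listed but not mapped to any analysis visit. The sentence is needed because the Day 8 window starts at Day 5, so these samples would otherwise have no stated destination. Calling them unscheduled would not exclude them, since SAP 4.5 maps unscheduled samples as well.

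A Day 1 sample with no recorded dosing time stays ambiguous, as it already does under Tables 2 and 3.

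The cost is one table cell and one sentence, and a few patients may lose a baseline value. The change is best made before treatment codes are opened.

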## **5. STATISTICAL ANALYSIS POPULATION**

### **5.1 Intent-to-Treat (ITT) Population**

The intent-to-treat (ITT) population will consist of all patients who are randomized in the study with confirmed SARS-CoV2 infection under protocol version 6.0 and above, regardless of whether or not they receive study treatment. This population will be used for primary analyses of efficacy. Patients will be analyzed in the treatment arm to which they were randomized and strata assignment at the time of randomization.

### **5.2 Efficacy evaluable (EE) Population**

The EE population is a subset of the ITT population, consisting of patients who did not die within 24 hours of randomization, had at least one post-baseline Ordinal Scale assessment, and received at least one dose of study treatment. Patients will be analyzed in the treatment arm to which they were randomized and strata assignment at the time of randomization.

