**Table 5: Application of Populations for Summary**

	ITT Population	EE Population	AT Population	PoC Population
Disposition	X			X
Baseline Characteristics				
Demographics	X	X	X	X
Medical history	X		X	X
Disease history	X		X	X
Prior/concomitant medication	X	X	X	X
Tobacco use	X	X	X	X
Drug exposure and compliance			X	X
Efficacy Endpoints				
Primary efficacy endpoint	X	X		X
Key secondary efficacy endpoints	X	X		X
Other secondary endpoints	X			X
Safety Endpoints				
TEAEs			X	X
Labs			X	X
Vital signs			X	X
ECG			X	X

CCI

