## 7. EFFICACY ANALYSES

Efficacy analyses will be primarily performed in ITT population. For primary and key secondary endpoints, efficacy analyses using the EE population will be considered as supportive for the corresponding analyses in the ITT population. Efficacy analyses in PoC population will be descriptive in nature.

Please refer to Table 6 below for efficacy endpoints and the corresponding definitions.

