**Table 6: Efficacy Endpoints and Definitions**

Endpoint	Definition
Primary Endpoint	
Day 14 Ordinal Scale improvement (OSI2-14)	Proportion of patients with at least a 2 points improvement (increase) in the Ordinal Scale by Day 14. Baseline score is defined as the last score measured before first dosing. The improvement is assessed between the baseline score and the latest score on or before Day 14, End of study (EoS) date, or database cut date, whichever occurs first.
Key Secondary Endpoints	
Time to an improvement of 2 points using Ordinal Scale (TTCI-2)	The time from randomization to an improvement of 2 points on the Ordinal Scale. For patients who didn't achieve clinical improvement of 2 points, 
 
If no death event by Day 28, they will be censored on the last contact date, on or before Day 28, EoS date, or database cut date, whichever occurs first.
 
 If they died by Day 28, they will be censored on Day 28.
Overall death rate on Day 28 (DR-28)	Proportion of patients died on or before Day 28.
Rate of mechanical ventilation (RMV)	Proportion of patients who ever used invasive mechanical ventilation or ECMO during the hospital stay.
Time to mechanical ventilation (TTMV)	Time to the first use of mechanical ventilation. For patients who never used mechanical ventilator, the censoring date is defined as the death date or last contact date (if no death), on or before EoS or database cut date, whichever occurs first.

Additional Secondary Endpoints	
Time to recovery (TTR)	Time to improvement from baseline score of 3 to $\geq 4$ or from a baseline score of 4 to $\geq 5$ by Day 28. For patients who didn't achieve recovery, the censoring rule will be the same as that in TTCI-2.
Day 7 Ordinal Scale 2 points improvement (OSI2-7)	Proportion of patients with at least a 2 points improvement (increase) in the Ordinal Scale from baseline to Day 7. The improvement is assessed between the baseline score and the latest score on or before Day 7, End of study (EoS) date, or database cut date, whichever occurs first.
Day 7 Ordinal Scale 1 point improvement (OSI1-7)	Proportion of patients with at least a 1 point improvement (increase) in the Ordinal Scale from baseline to Day 7. The improvement is assessed the same as in OSI2-7.

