## 7.2 Analyses of Secondary Efficacy Endpoints

### 7.2.1 Analyses of Key Secondary Efficacy Endpoints

If the primary endpoint, OSI2-14, is significant in ITT population, the following key secondary endpoints in ITT population will be sequentially tested in the order listed below. If any null hypothesis is not rejected in this sequence of tests, formal sequential testing will be stopped and the analyses of any endpoints thereafter will be nominal only.

- Time to clinical improvement (TTCI-2)
- Overall Death rate on Day 28 (DR-28)
- Rate of mechanical ventilation (RMV)
- Time to mechanical ventilation (TTMV)

For binary endpoints (DR-28, RMV), the difference in rates between treatment arms will be calculated with a 95% confidence interval (CI). Comparison between 2 treatment arms will be performed using the Cochran-Mantel-Haenszel (CMH) test stratified by the randomization stratification factors. The CMH estimate of the odds ratio and its 95% CI and the p-value for testing the treatment difference will be reported.

For time to event endpoints (TTCI-2, TTMV), the number and percentage of patients with the corresponding events will be reported. Median event times with 95% CIs will be estimated by Kaplan-Meier (KM) method for each treatment arm. KM curves by treatment arms will be provided.

The following analysis stratified on randomization strata will be performed:

- Log-rank test stratified to compare the event times between treatment arms

- Hazard ratios of treatment effect with 95% CI estimated by Cox proportional hazards model with Efron's method of tie handling

Non-stratified log rank test and Cox proportional hazards model will be performed as sensitivity analyses.

The Kolmogorov-type Supremum test will be conducted to assess the validity of the proportion hazards assumption in all fitted Cox proportional hazards models. If there is evidence for a violation of the proportional hazards assumption, interaction terms between time-dependent terms and treatment variable (selinexor vs. placebo) will be added to assess time-varying treatment effects.

In sensitivity analysis for RMV, analyses will be conducted with patients who ever used one of the respiratory assistances as below:

- Non-invasive positive pressure mechanical ventilation (CPAP/BiPAP)
- High-flow nasal cannula
- Invasive mechanical ventilation
- Extracorporeal membrane oxygenation (ECMO)

For TICI-2, sensitivity analyses will be performed in the same manner as OSI2-14.

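### The supportive efficacy-evaluable analysis of the Day 28 death rate leaves out patients who die within 24 hours of randomization; the ITT analysis and the formal test are unaffected

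*SAP*

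**What the plan says.** SAP 5.2 builds the EE set from ITT by three conditions, all of them determined after randomization. It keeps "patients who did not die within 24 hours of randomization, had at least one post-baseline Ordinal Scale assessment, and received at least one dose". No reason is given for the survival condition. Protocol 9.3 defines only the ITT and all-treat sets, so EE appears in the SAP alone.

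SAP 7 gives EE its role: "For primary and key secondary endpoints, efficacy analyses using the EE population will be considered as supportive". Table 5 has a single row, "Key secondary efficacy endpoints", marked for ITT, EE and the proof-of-concept set.

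DR-28 is a key secondary endpoint in both documents and the second of four in the SAP 7.2.1 test sequence. Table 6 defines it as "Proportion of patients died on or before Day 28", with no exception for early deaths. SAP 5.1 makes ITT the set for the primary efficacy analyses, and SAP 7.2.1 places the sequential tests in ITT.

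**The concern.** A patient who dies on the first day has a complete DR-28 observation, so nothing about that patient prevents evaluation. Dropping the patient from a death-rate analysis selects on the outcome itself.

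The rule is not confined to patients who were never treated. Protocol 4.4 puts randomization before dosing, and Protocol 3.1 recommends dosing within 12 hours of consent, so a patient can be randomized, dosed and die inside 24 hours. Because EE already requires a dose, what the survival condition adds is the removal of treated patients who die early and have a post-baseline score. Treatment could affect that outcome.

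What is at stake is how the supportive result is read. Its purpose is to show whether the ITT mortality finding is robust. The survival condition makes it depart from ITT when early deaths are unequal between arms, and the departure favours the arm that had more of them. A difference between the EE and ITT results would then partly reflect the set definition.

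**Working it through.** **No plan figure to reproduce.** Neither document states an EE size, a number of early deaths or an expected Day 28 mortality. The basis for the sample size is redacted and is not needed here.

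**Inputs**
- Planned ITT size: about 247 (Protocol 9.6).
- Allocation: about the first 50 ITT patients at 2:1 and the rest at 1:1 (SAP 7.1.1). Selinexor: 50 × 2/3 + 197/2 = 131.8, taken as 132. Placebo: 50/3 + 197/2 = 115.2, taken as 115.
- Assumed, not in the documents: Day 28 mortality of 5–20%, the same in both arms up to rounding, and 0 to 5 early deaths in an arm.

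**Effect of the 24-hour condition alone.** With D deaths among N patients in an arm, k of them within 24 hours:
- ITT rate = D/N
- EE rate = (D − k)/(N − k)
- fall in the arm's rate = k(N − D) / [N(N − k)], which is positive whenever anyone survives.

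Example at 10% mortality, 13 selinexor and 12 placebo deaths, one early death on selinexor only. The selinexor rate goes from 13/132 = 9.85% to 12/131 = 9.16%. The placebo rate stays at 12/115, so the risk difference shifts by −0.69 points.

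Shift in the risk difference (selinexor minus placebo, percentage points), by number of early deaths dropped:

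| Assumed mortality | Deaths (sel / pbo) | 1 sel only | 1 pbo only | 1 in each arm | 3 sel only | 5 sel only |
|---|---|---|---|---|---|---|
| 5% | 7 / 6 | −0.72 | +0.83 | +0.11 | −2.20 | −3.73 |
| 10% | 13 / 12 | −0.69 | +0.79 | +0.10 | −2.10 | −3.55 |
| 15% | 20 / 17 | −0.65 | +0.75 | +0.10 | −1.97 | −3.34 |
| 20% | 26 / 23 | −0.61 | +0.70 | +0.09 | −1.87 | −3.16 |

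One unmatched early death moves the comparison by about 0.6–0.8 points. One in each arm moves it by about 0.1.

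**Effect of the other two conditions.** Requiring a dose and a post-baseline score can remove deaths, for example a death before dosing, which acts as above. It can also remove survivors. Dropping m survivors gives D/(N − m), which exceeds D/N. One survivor dropped from selinexor at 10% mortality takes 13/132 = 9.85% to 13/131 = 9.92%, a rise of just under 0.1 point. The direction of the whole EE rule is therefore not fixed in advance.

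**The case against.** The strongest answer is that no decision rests on this analysis. SAP 7 says that "efficacy analyses using the EE population will be considered as supportive for the corresponding analyses in the ITT population", and the formal test of DR-28 keeps every early death. Mortality is also reported elsewhere without EE: overall survival and the Day 14 death rate fall in the Table 5 row marked for ITT and the proof-of-concept set only, and SAP 8.1 adds an overview and a listing of deaths. Any gap between EE and ITT would be visible. A prespecified set of treated patients with follow-up is a legitimate companion to ITT. Such deaths should also be rare: Protocol 4.2 excludes critical disease and, under criterion 2, patients the investigator thinks will not live 48 hours from screening.

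All of that stands, and it limits the consequence. It does not supply a reason to exclude deaths from a death rate, and nothing in either document exempts DR-28 or adds those deaths back. Criterion 2 makes early deaths few but does not rule them out. It is a judgement dated from screening, which Protocol Table 1 allows up to two days before Day 1.

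Two stronger readings are tempting and unsupported:
- A reader might infer that deaths are lost from the confirmatory mortality result, or that type I error is affected. SAP 5.1 and 7.2.1 place that analysis in ITT, so neither follows.
- A reader might infer that EE can only lower each arm's death rate. That is true of the 24-hour condition taken alone. The dose and post-baseline-score conditions can remove survivors and raise the rate.

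**Conclusion.** The point holds for one supportive analysis and is minor. As written, the EE analysis of DR-28 excludes patients because they had the outcome. The distortion is about 0.6–0.8 percentage points in the risk difference per unmatched early death, about 1.9–2.2 points for three on one arm, and close to nil when exclusions balance. These sizes rest on assumed mortality of 5–20% and arms of about 132 and 115, and they would shrink if sample size re-estimation enlarges the trial. With no early death, the 24-hour condition has no effect. The objection is to using this set for DR-28, not to having an EE set.

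**What to change.** In SAP 7 and Table 5, split the key secondary row: analyse DR-28 in ITT only, and keep EE as supportive for TTCI-2, RMV and TTMV. This needs one sentence in SAP 7 and one extra table row.

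If a supportive EE analysis of DR-28 is wanted, count every death that EE excludes as an event, whether it came within 24 hours, before dosing or before a post-baseline score, and report EE exclusions by arm and reason. Those deaths then return to numerator and denominator and the shift they cause is zero. Survivors without a dose or a score would still be left out, which is why the exclusions should be tabulated.

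Deleting only the 24-hour condition would not be enough, because a patient who dies before dosing would still be dropped.

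The cost is small: one supportive table is lost, or its set moves slightly closer to ITT. No new data are needed and the formal tests do not change.
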